#### 5.4.3.5 Food Allergy Quality of Life Questionnaires Parent Form (FAQLQ-PF)

The FAQLQs are disease-specific health-related quality of life questionnaires for subjects with food allergy. They are considered reliable and valid instruments to measure the impact of food allergy on health-related quality of life.

At screening and at Month 12, the subjects' parents/guardians will complete the FAQLQ-PF questionnaires (in countries where the translated and validated questionnaires are available and used).

Starting from protocol v6.0, a new version of the FAQLQ-PF questionnaire will be used for subjects randomized in Part B, at screening and at Month 12. The template of the questionnaire is provided in Appendix 6 of the protocol.

FAQLQ-PF will be analyzed according to the 3 following domains:

- EI: Emotional impact (Q no: 2, 6-7, 9-11),
- FA: Food-related anxiety (Q no: 1, 4-5),
- SDL: Social and dietary limitations (Q no: 3, 8, 12-14).

Age at Visit 1 will be used to define which questions will be applicable during the study for each subject. Questions not needed will be not used for analysis.

The following instructions from the reference website ([www.faqlq.com](http://www.faqlq.com)) will be used for the derivations of (sub-) scales:

- 1) Each question of the FAQLQ-PF is answered on a 7-point scale (0 to 6) and will be recoded 1 to 7
- 2) All sub-scores are calculated by dividing the sum of scores by the number of completed questions
- 3) FAQLQ-PF Total Score = (EI Subscale Score + FA Subscale Score + SDL Subscale Score) / 3
- 4) If > 20% of items in any (sub-) scale are missing then the respective (sub-) scale is set to missing
- 5) Total score is calculated only if the 3 sub-scores are completed

CONFIDENTIEL / Ne pas diffuser sans autorisation de DBV

CONFIDENTIAL / Do not distribute without DBV authorization

	Statistical Analysis Plan	
	EPITOPE (V712-304) – Statistical Analysis Plan	
	Référence du Document /Document Reference : CCI	Page : 47 / 74

CCI

The FAQLQ Parent Form (FAQLQ-PF) total score and the Emotional impact domain score at baseline (V1) and Month 12 and the change from baseline at Month 12 will be summarized descriptively by treatment group as continuous data. This analysis will be repeated in the subgroup of responders vs non-responders as per Primary endpoint definition.

Absolute change in FAQLQ-PF total score and each domain scores will be analyzed using ANCOVA models with treatment group as fixed effects and respective baseline value as a covariate. From the statistical model, LS Means, corresponding 2-sided 95% CI, and the LS Mean difference (DBV712 250µg – Placebo) and corresponding 2-sided 95% CI, effect size and p-value from the 2-sided test of no difference between treatment groups will be presented.

All analyses will be performed on the FAS using observed data, with no imputation of missing data. Data will also be listed.

#### 5.4.3.6 Food Allergy Independent Measure Parent Form (FAIM-PF)

The FAIM-PF questionnaires capture the subjects' expectation of something happening because of her/his food allergy. It corresponds to the Section E of the FAQLQ-PF questionnaire.

Each question of the FAIM-PF is answered on a 7-point scale (0 to 6) and will be recoded 1 to 7. Total FAIM-PF scores will be calculated by dividing the sum of completed items by the number of completed items. Total FAIM-PF scores range from 1 "low perceived disease severity" to 7 "high perceived disease severity". Calculation of total FAIM-PF scores will be done only when 80% or more of the items are completed.

Some specific items mentioned below must be reverse coded.

There are 2 sections in the questionnaire with the same question, one from the perspective of the parents (What chance do you think your child has of.....?) the other reflecting the thoughts of the child (What chance does your child think he/she has of.....?). Both mean scores of the parent's form ("Parent's thoughts" and "Child's thoughts") are calculated as the mean of the single items, only if none of the items is missing. In both scores question 4 will be reverse scored.

The total FAIM-PF-scores will be summarized overall and for each type of questionnaire, in total and by randomized treatment group (Placebo/DBV712 250µg) at baseline (V1) and Month 12, and the change from baseline at Month 12.

Absolute change in FAIM-PF total score and for each type of questionnaire will be analyzed using ANCOVA models with treatment group as fixed effects and respective baseline value as a covariate. From the statistical model, LS Means, corresponding 2-sided 95% CI, and the LS Mean difference (DBV712 250µg – Placebo) and corresponding 2-sided 95% CI, effect size and p-value from the 2-sided test of no difference between treatment groups will be presented.

All analyses will be performed on the FAS using observed data, with no imputation of missing data. Data will also be listed.

## 5.5 Study Drug Safety Evaluation

Safety analysis will be performed using the Safety Set (SAF). All outputs will be summarized by actual treatment received and presented by treatment group and overall. Unless otherwise specified, missing data will not be replaced/imputed.

CONFIDENTIEL / Ne pas diffuser sans autorisation de DBV

CONFIDENTIAL / Do not distribute without DBV authorization

	Statistical Analysis Plan	
	EPITOPÉ (V712-304) – Statistical Analysis Plan	
	Référence du Document /Document Reference : CCI	Page : 48 / 74

CCI

### 5.5.1 Adverse Events

#### 5.5.1.1 Definitions

**Treatment-emergent AEs** will be defined as any AEs, regardless of relationship to IMP reported during or after the initial application, i.e. AEs where start date/time is on or after date/time of the first study treatment.

- When an AE's start date is equal to the date of first study treatment and the start time of AE is missing, AE will be defined as treatment emergent.
- Where dates are missing or partially missing, adverse events will be assumed to be treatment-emergent, unless there is a clear evidence (through comparison of partial dates) to suggest that the adverse event started prior to the first study treatment. More specifically, See Section 5.5.1.2.

AEs occurring after the end of the study will be recorded only if the investigator considers that there is a causal relationship with the IMP and as such, will be considered also as TEAEs.

**Pre-treatment emergent AE** will be defined as an AE that begins before the first administration of IMP.

**IMP-induced Local TEAEs** are defined as TEAEs considered as related to IMP with a High-Level Term equal to "Application and instillation site reactions" and will be flagged in the analysis datasets.

Following medication use will be defined:

- **Epinephrine use** will be identified by a combination of standard medication name that contains "EPINEPHRINE" and ATC level 1 = "CARDIOVASCULAR SYSTEM".
- **Systemic or inhaled corticosteroid use** will be identified by:
  - ATC code starting with "H02"
  - ATC code starting with "R03AK" (Adrenergics in combination with corticosteroids or other drugs, excl. anticholinergics) and "R03BA" (Glucocorticoids)
- **Topical corticosteroid use** will be identified by ATC code starting with "D07" (Corticosteroids, Dermatological preparations)

Treatment emergent adverse events of special interest (AESI), are defined as:

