### Safety Analyses:

#### Adverse Events

TEAEs will be defined as any AEs, regardless of relationship to IMP, which occur during or after the initial patch application or any event already present that worsens in either severity or relationship to DBV712 or placebo.

An overall summary of TEAEs will be provided showing the number and percentage of subjects with any TEAEs, any potentially drug-related TEAEs, any DBV712-induced Local TEAE, any severe DBV712-induced local TEAE, any severe TEAEs, any severe potentially drug-related TEAEs, any serious TEAEs, any potentially drug-related serious TEAEs, any

TEAEs leading to discontinuation and any TEAEs leading to death. The number of events will also be presented.

The number of TEAEs, as well as the number and percentage of subjects who experienced at least one TEAE will be summarized by SOC and PT.

The incidence of the following events will be summarized:

- TEAEs by maximum severity, by duration and by relatedness to Viaskin® patch;
- Local skin reactions at sites of Viaskin® patch application as assessed by the subjects (incidence, duration and severity, 0 to 3 grading scale);
- Local skin reactions at sites of Viaskin® patch application as assessed by the Investigator (severity, 0 to 4 grading scale at each time point);
- SAEs, serious TEAEs and serious potentially IMP-related TEAEs;
- Potentially IMP-related TEAEs;
- TEAEs leading to study treatment discontinuation and TEAEs leading to epinephrine intake;
- Local and systemic AESIs.

Additionally, the proportions of patches during the one-year exposure period that led to mild, moderate or severe TEAE considered related to Viaskin® patches, will be summarized.

All AEs will be listed as well as SAEs and TEAEs leading to an epinephrine intake.

The reactions induced by a DBPCFC because they are expressly provoked, will be differentiated from those AEs occurring outside of a challenge. Objective and subjective symptoms/reactions elicited during a challenge will be summarized separately:

- Symptoms elicited during a peanut food challenge by severity;
- SAEs elicited during a peanut food challenge.

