#### 6.2.1.2 Definitions

An AE is any untoward medical occurrence that occurs in a subject or clinical investigation subject administered a pharmaceutical product, and which does not necessarily have a causal relationship with this treatment. An AE can therefore be any unfavorable and unintended sign (including abnormal laboratory finding), symptom, or disease temporally associated with the use of an investigational product, whether or not considered related to the investigational product.

All AEs, including intercurrent illnesses, occurring during the study will be documented in the e-CRF. Concomitant illnesses, which existed before entry into the study, will not be considered AEs unless they worsen during the treatment period. All AEs, regardless of the source of identification (for example physical examination, laboratory assessment, electrocardiogram [ECG], reported by subject), must be documented.

Pre-existing conditions will be recorded in the e-CRF on the Medical History or appropriate page.

Adverse events due to DBPCFC will also be recorded in the e-CRF but will be analyzed separately.

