### 8.6.1 Adverse Events

Treatment-emergent AEs will be defined as any AEs, regardless of relationship to IMP, which occur during or after the initial Viaskin® patch application or any event already present that worsens in either severity or relationship to IMP following exposure to Viaskin® patches.

All AEs will be reported by SOC and PT and coded using the latest available version of the MedDRA dictionary.

An overall summary of TEAEs will be provided showing the number and percentage of subjects in each treatment group with any TEAEs, any potentially drug-related TEAEs, any DBV712-induced local TEAE, any severe DBV712-induced local TEAE, any severe TEAEs, any severe potentially IMP-related TEAEs, any serious TEAEs, any potentially IMP-related serious TEAEs, any TEAEs leading to discontinuation, any TEAEs leading to epinephrine intake and any TEAEs leading to death. The number of events will also be presented.

The number of events as well as the number and percentage of subjects who experienced at least one event will be summarized by SOC, PT and treatment group. The incidence of the following events will be summarized:

- TEAEs (distinguished from symptoms/reactions elicited during the DBPCFCs): incidence, maximum severity and duration;
- Local skin tolerance at sites of Viaskin® patch application as assessed by the subjects (incidence, duration and severity) (see Section 8.6.5);

- Local skin tolerance at sites of Viaskin® patch application as assessed by the Investigator (severity) (see Section 8.6.6);
- SAEs, serious TEAEs and serious potentially IMP-related TEAEs;
- Potentially IMP-related TEAEs;
- TEAEs leading to study treatment discontinuation and TEAEs leading to epinephrine intake;
- Local AESIs and systemic AESIs (see Section 6.2.1.3.5) .

Additionally, the proportions of patches during the one-year exposure period that led to mild, moderate or severe TEAE considered related to IMP will be summarized.

All AEs will be listed. SAE and TEAE leading to an epinephrine intake will also be listed separately.

The reactions appearing during a DBPCFC (as they are expressly provoked) will be differentiated from those AEs occurring outside of the DBPCFC. Objective and subjective symptoms/reactions elicited during the DBPCFCs in the different treatment groups (see Section 6.1.1 for full details) will be summarized separately.

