**AE start date**

- If AE start date is missing, the AE start date will not be imputed.
  - If derived AE end date is missing, the AE will be considered as TEAE
  - If derived AE end date is before (<) the Treatment start date, the AE will be considered as pre-TEAE
  - If derived AE end date is on or after (≥) the Treatment start date, the AE will be considered as TEAE
- If AE start date is partial:
  - If derived AE end date is missing:
    - If AE start day is missing it will be imputed to “01” unless month and year are the same as month and year of the TRT start date then impute TRT start date
    - If AE start day/month are missing they will be imputed to “01JAN” unless year is the same as year of the TRT start date then impute TRT start date
  - If derived AE end date is before (<) the Treatment start date:
    - Missing day will be imputed to 01 and Missing month will be imputed to “JAN”
  - If derived AE end date is on or after (≥) the Treatment start date:
    - If AE start day is missing it will be imputed to “01” unless month and year are the same as month and year of the TRT start date then impute TRT start date
    - If AE start day/month are missing they will be imputed to “01JAN” unless year is the same as year of the TRT start date then impute TRT start date

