- By maximum duration: For these tables TEAEs will be presented by SOC, PT within each SOC and maximum duration within each PT (using the classes for duration in days: (1 to 7 Days, 8 to 15 Days, 16 to 30 Days, 31 to 60 Days, 61 to 90 Days, More than 90 Days). For AEs ongoing at the end of the study, duration will be imputed based on the date of subject end of study. For AEs not ongoing but with missing end date, duration will be imputed based on date of last study treatment.

Additionally, for TEAEs and TEAEs considered related to IMP, tables showing number of subjects, percentage of subjects and number of events by severity will be provided. Subjects will be counted once per SOC, per PT and per severity. For these specific tables, if the severity is missing, no hypothesis will be assumed to replace the missing severity.

Adverse event summaries will be ordered in terms of decreasing frequency for SOC, and PT within SOC, in the active treatment group, and then similarly by decreasing frequency in the placebo group, and then alphabetically for SOC, and PT within SOC.

A by-subject listing of all adverse events will be provided. This listing will be presented by treatment group and will include: treatment group, subject identifier, age, sex, adverse event (SOC, PT, and verbatim term), date/time of onset (and corresponding study day), date/time of resolution (and corresponding study day), duration, severity, treatment required, relationship to IMP, relationship to an accidental peanut consumption, relationship to DBPCFC, and AESI flag, and action taken with the IMP, outcome, and whether the event is classified as serious or not with the corresponding criteria.

Pre-treatment emergent adverse events will be listed separately the same way as the treatment emergent adverse events.

TEAE leading to an epinephrine intake will also be listed.

Finally, SAEs will also be listed the same way with an additional flag for treatment emergent SAEs.

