## 5.11 Changes in the Analyses planned in protocol

The following changes have been done compared to the analyses described in the protocol:

- Farrington-Manning 95% confidence interval (CI) method is used instead of Newcombe method for the difference in response rates, to allow multiple imputation. This change has no impact on the study power.
- Intercurrent events have been detailed for primary and secondary analyses.
- Additional sensitivity, other efficacy and subgroup analyses have been added.
- Safety will also be assessed by subgroups.
- Additional analysis on DBPCFC symptoms have been added.
- AESI identification has been updated.

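### The SAP defines treatment-emergent AEs by start date alone, dropping without declaration the protocol's rule that already-present events worsening after exposure also count; probably few events are affected

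*SAP*

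**What the plan says.** The protocol gives the TEAE definition twice, in the synopsis (Safety Analyses) and in section 8.6.1, each time with two limbs. The first covers AEs that occur at or after the first patch application. The second covers, in 8.6.1, "any event already present that worsens in either severity or relationship to IMP following exposure to" the patches and, in the synopsis, "any event already present that worsens in either severity or relationship to DBV712 or placebo".

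SAP 5.5.1.1 keeps the first limb only and turns it into a date test: "AEs where start date/time is on or after date/time of the first study treatment". It then creates a complementary class, the pre-treatment emergent AE, which "will be defined as an AE that begins before the first administration of IMP". No exception is made for later worsening. SAP 5.5.1.3 gives that class a listing only: "Pre-treatment emergent adverse events will be listed separately the same way as the treatment emergent adverse events".

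SAP 5.11 lists six changes from the protocol. The TEAE definition is not one of them; the nearest item is "AESI identification has been updated", which concerns a different class of event. The SAP modification history does not record the change either.

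**The concern.** The two documents define the main safety outcome differently, and nothing tells the reader that the SAP is narrower. The overview, SOC/PT, relatedness, severity, duration, discontinuation, epinephrine and corticosteroid tables in SAP 5.5.1.3 are all built on TEAEs, so an event that fails the flag is absent from all of them.

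The omitted class is relevant in this population. Asthma at GINA Step 1 or 2 is permitted at entry. Atopic dermatitis is excluded only when it is generalized disease leaving no intact skin for the patch. The SAP repeats the TEAE overview in children with ongoing asthma or eczema at baseline, and any lost events would tend to fall in those subgroups.

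**Working it through.** The point rests on no sample size, power or other figure, so the check is a comparison of rules.

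**Step 1: does another SAP rule restore the worsening limb?** It does not. The rules in SAP 5.5.1.1 and 5.5.1.2 deal only with missing or partial dates. If the start date is wholly missing, "the AE start date will not be imputed", and the event is a TEAE when its end date is missing or falls on or after treatment start. A partial start date matching the month and year of treatment start is set to the treatment start date, provided the end date is missing or not before treatment. These rules lean towards inclusion but do not depend on worsening. An event with a complete pre-dose start date and documented worsening on treatment is excluded.

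**Step 2: which pre-dose events can reach the AE dataset?** Three protocol rules narrow the set.
- Section 6.2.1.4: from consent through Day -1, only SAEs are entered in the e-CRF. Other screening AEs stay in source documents.
- Section 6.2.1.4: from the day of first dose, all AEs are entered. This includes an event that starts on Day 1 before the patch goes on.
- Section 6.2.1.2: illnesses present before study entry "will not be considered AEs unless they worsen during the treatment period". Until then they belong in medical history.

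None of these says whether the onset date of a worsened condition is its original onset or the date it worsened.

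**Step 3: apply both definitions to the possible cases.**

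| Event that worsens after the first patch | Protocol | SAP 5.5.1.1 |
|---|---|---|
| Pre-existing condition, entered as a new AE dated at the worsening | TEAE | TEAE |
| Pre-existing condition, entered with its original onset date | TEAE | Pre-treatment, listed only |
| Screening SAE that persists and worsens, kept as one record | TEAE | Pre-treatment, listed only |
| Day 1 event with a recorded time before the patch | TEAE | Pre-treatment, listed only |
| Day 1 event with no recorded time | TEAE | TEAE by default |

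SAEs elicited by the entry food challenge fall outside the third row in practice. SAP 5.5.1.3 removes them from the AE analyses, and SAP 5.6.1 tabulates them separately.

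**Step 4: can worsening be derived from the data?** The AE fields listed in protocol 6.2.1.4 include onset, resolution, severity, relationship, action taken and outcome. They include no date of severity change and no earlier grade. By contrast, 6.2.1.3.6 collects the time of grade change for food-challenge symptoms. A worsening flag therefore cannot be programmed from a single AE record with those fields alone; it needs a dating rule and a review step.

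**The case against.** The strongest reply is that data capture already does most of what the missing limb is for. Only SAEs are entered during screening. A pre-existing illness becomes an AE only by worsening on treatment, so its natural onset date is on treatment and it passes the SAP's test. In Part B, asthma aggravation and application-site eczema are solicited under their own terms at each visit and phone contact, and an event entered that way would carry its own date. Change in atopic dermatitis is also tracked by SCORAD. Events classed as pre-treatment stay in the all-AE and pre-treatment listings and, if serious, in the SAE listing. The entry convention may be set out in the e-CRF completion guidelines, which are not among the documents supplied.

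Most of this stands, and it bounds the size of the problem. It does not empty the affected set, because three of the five cases above still diverge and no supplied document tells sites which onset date to use. SCORAD covers one condition only and gives no relatedness or action taken.

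A reader might infer more: that worsening events are generally lost from the TEAE tables, or that the active arm's counts are biased downwards relative to placebo. The documents support neither. The first would require sites to enter worsenings under the original onset, which no text instructs. The second would also require treatment to aggravate existing disease, and there is no figure from which to size it.

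**Conclusion.** The SAP contradicts the protocol's TEAE definition and does not declare that it does. For worsened events with a known pre-dose onset, the SAP rule can only lower TEAE counts relative to the protocol. Those events move from tables to listings; they do not leave the report.

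The number affected cannot be derived from the documents. It is probably small, given the limits on which pre-dose events enter the e-CRF. It is zero if every worsening is recorded as a new AE dated at the worsening. No between-arm bias can be quantified. The correction is worth making because the definition should not depend on an unstated site convention, and because it is cheap.

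**What to change.** In SAP 5.5.1.1:
- Restore the second limb, so that a TEAE is an AE starting on or after the first application, or one already present that worsens in severity or in relationship to IMP afterwards.
- Exclude such events from the pre-treatment class.
- State that a worsening of a pre-existing event is handled as an AE whose onset, for the TEAE flag, is the date of worsening.

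Because the listed AE fields hold no date of severity change, add a check at the blinded data review before lock: review every AE that has a pre-dose onset and continues after the first application, and settle its classification. If the narrower definition is intended, declare and justify it in SAP 5.11 instead.

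The cost is a text change, a derivation rule and a small review task. TEAE counts may rise slightly. If sites already date worsenings as new AEs, the tables do not change.

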#### 6.2.1.4 Recording Adverse Events

Adverse event reporting will start at the signature of the informed consent form (ICF) and end after the 2-week follow-up period (Visit 12: End of Study Visit).

During the screening period (that is, from the time of ICF signature through Day-1), only SAEs will be recorded in the e-CRF; and AEs that do not meet any seriousness criteria will only be documented in the subject's source documents.

Adverse events occurring after the end of the study should be reported to the Sponsor by the Investigator if the Investigator considers that there is a causal relationship with the IMP.

Adverse events still ongoing at the time of the End of Study Visit will be followed up for an additional 30 days, or until they resolve or stabilize, whichever comes first.

All AEs occurring on or after the day of the first dose of IMP, regardless of the relationship to the IMP, will be recorded in the e-CRF.

All AE reports in the e-CRF should contain the following information of the event: date and time of onset, date and time of resolution, severity, treatment required, relationship to IMP, action taken with the IMP, outcome, and whether the event is classified as serious or not.

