#### ***7.2.10 Visit 11 (≤1 week after Visit 10), End of Treatment Period***

Visit 11 corresponds to the end of the 12-month treatment period. Patch application ends at this visit. The patch worn by the subject when she/he arrives to this visit is removed and there will be no further patches applied beyond Visit 11.

For the subjects who will accept to participate in the extension study, the Visit 12 will be cancelled. The inclusion in the study extension will occur at the end of the Visit 11.

Visit 11 corresponds to the second day of the post-treatment DBPCFC after 12 months of treatment. It takes place within a week following the first day of the post-treatment DBPCFC.

The following assessments will be performed at this visit:

- Physical examination (including a complete skin examination; to take place before DBPCFC; see Section 6.2.4);
- Vital signs (to take place before DBPCFC; see Section 6.2.3);
- Post-treatment DBPCFC (second day) (see Section 6.1.1); the patch should be removed before performing the DBPCFC;
- AEs recording (including volunteered or solicited AEs, AESIs and recording of AEs/allergies in response to the DBPCFC);
- Concomitant medications (including any medications given to treat allergic symptoms) (see Section 5.7);
- Check for any accidental peanut consumption (see Section 6.4.4);
- Collect and check that the subject diary has been completed accurately. The diary will not be given back to the subject;
- Collect the treatment box dispensed at the Visit 10 (Month 12 visit), check the unused medication and assess medication compliance;

- Patch adhesion Investigator's assessment: made with the patch still applied, the Investigator assesses the adherence of the patch to the skin as well as the occlusion of the patch chamber. Any issues reported by the subjects' parents/guardians related to the patches application or removal will also be reported;
- Check skin reactions under or around the current patch (without removing it) and all other zones of application and grade severity of the skin reactions (see Table 3, Section 6.2.6);
- Take a photograph of the sites of application of the Viaskin® patch, load it onto the study server (described in section 6.2.6) and keep it in the subject's medical records or source documents; download the photographs taken by the parents' subject from the camera memory card or the device, if any photos were taken since the previous visit and review them;
- Schedule Visit 12.

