- Any treatment-emergent systemic AESI considered related to IMP (reported as related, probably or possibly related):
  - Reported as Anaphylactic reaction
  - Reported as Systemic hypersensitivity reaction leading to epinephrine intake
- Any TEAEs leading to an epinephrine intake
  - Considered related to IMP
  - Considered unrelated to IMP,
- Any TEAEs leading to systemic or inhaled corticosteroid use,
- Any TEAEs leading to topical corticosteroid use

Overall overview of TEAEs will be repeated:

- for the subgroups listed in section 5.2.5,
- including APC,
- for subperiod of treatment post 4 years old (from the date turning 4 years old to end of treatment).

The number and percentage of subjects who experienced at least one event and the number of events will further be summarized by SOC and PT for the following types of events:

- any TEAEs,
- any serious TEAEs,
- any potentially drug-related TEAEs,
- any serious potentially drug-related TEAEs,
- any TEAEs leading to permanent study treatment discontinuation,
- any TEAEs leading to temporary study treatment discontinuation,
- any TEAEs leading to death,
- any TEAEs leading to epinephrine intake,

CONFIDENTIEL / Ne pas diffuser sans autorisation de DBV

CONFIDENTIAL / Do not distribute without DBV authorization

	Statistical Analysis Plan	
	EPITOPÉ (V712-304) – Statistical Analysis Plan	
	Référence du Document /Document Reference : CCI	Page : 53 / 74

CCI

- any TEAEs leading to systemic or inhaled corticosteroid use,
- any TEAEs leading to topical corticosteroids use
- any TEAEs occurring after 407 days (V10 (365 + 7 days) + V11 (7 days) + V12 (4 weeks)).

Additional tables will be created to display the most frequent TEAEs (by preferred term), occurring in at least 5% of the subjects in any of the treatment groups.

For TEAEs and TEAEs considered related to IMP, additional tables will be provided showing number of subjects and percentage of subjects:

- By maximum severity (severe, moderate and mild): Subjects will be counted once per SOC and once per PT at the worst severity. If the severity is missing, the worst severity will be assumed.

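### The table of TEAEs after Day 407 uses every child in the arm as denominator, although only children still in the study by then have all their adverse events recorded

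*SAP*

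**What the plan says.** **Recording during the study.** Protocol 6.2.1.4 requires that adverse events from the day of first dose onwards, "regardless of the relationship to the IMP, will be recorded in the e-CRF". Routine reporting is to "end after the 2-week follow-up period (Visit 12: End of Study Visit").

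**Recording afterwards.** The same section says "Adverse events occurring after the end of the study should be reported to the Sponsor by the Investigator if the Investigator considers" that the IMP caused them. SAP 5.5.1.1 repeats the rule: "AEs occurring after the end of the study will be recorded only if the investigator considers that there is a causal relationship with the IMP". It then gives these events TEAE status: "and as such, will be considered also as TEAEs".

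**TEAE window.** SAP 5.5.1.1 opens the window at first treatment ("AEs where start date/time is on or after date/time of the first study treatment") and sets no closing date. Protocol 8.6.1 is open-ended in the same way.

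**The late table.** Among the summaries by SOC and PT, giving subjects, percentages and events, SAP 5.5.1.3 lists "any TEAEs occurring after 407 days (V10 (365 + 7 days) + V11 (7 days) + V12 (4 weeks")). It does not limit the table to children still in the study, split events by onset before or after study end, or define a denominator of its own. The general convention in SAP 5.1 therefore applies, and percentages are taken over all subjects in the treatment group.

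**Children past schedule.** SAP 3.1.3 and 5.3.8 expect Covid-19 postponements to carry some children beyond the planned duration. SAP 5.3.8 has exposure classes of 12 to 18 months and above 18 months. SAP 5.2.6.1 derives a study end date for each child, but the TEAE definition does not use it.

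**The concern.** A table of events after the scheduled end of study invites one reading: how often children kept on the patch or under observation for longer than planned had adverse events. As specified, it does not answer that question. Its numerator takes all events from delayed children and only related events from everyone else. Its denominator counts everyone, including children who finished on time or stopped early and for whom an unrelated event after Day 407 could not have been recorded. The percentage would understate the event frequency in children actually followed past Day 407. It would also add a second group of cases selected by the investigator's causality judgement.

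**Working it through.** **Step 1: reproduce the cut-off.** From the terms in SAP 5.5.1.3: 365 + 7 (Visit 10 window) + 7 (Visit 11) + 28 (Visit 12) = 407. This reproduces the SAP's figure, which is the last day on which an on-schedule child can have Visit 12.

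**Step 2: when an on-schedule child leaves.** Visit 10 falls on Days 358 to 372. Visit 11 is at least one day and at most seven days later, so Days 359 to 379. Visit 12 is 28 days after that, so Days 387 to 407. Children entering the extension have no Visit 12 ("The inclusion in the study extension will occur at the end of the Visit 11"), so I take their study end as Visit 11, by Day 379. No on-schedule child is under full recording after Day 407.

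**Step 3: how far a delayed child can run.** SAP Table 2 accepts Visit 10 to 365 + 90 = Day 455, Visit 11 to 455 + 14 = Day 469, and the end-of-study visit to 469 + 56 = Day 525. These are analysis windows, not limits on stay, but they show that the SAP foresees full follow-up well past Day 407.

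**Step 4: set the two groups side by side.**

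| Child after Day 407 | Unrelated AE | Related AE | In the denominator? |
|---|---|---|---|
| Still in the study (until own study end) | recorded | recorded | yes |
| Already out of the study | not recorded | recorded if reported | yes |

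**Step 5: illustrate the effect.** The documents give no inputs, so all three below are assumptions.

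- *f*: share of children still in the study after Day 407, 5% to 50%.
- *p*: share of those with any AE after Day 407, 30% to 60%.
- *r*: share of the other children with a reported related AE after Day 407, 0% to 3%.

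Table percentage = *f p* + (1 − *f*) *r*. Share of counted children who are there under the related-only rule = (1 − *f*) *r* / table percentage.

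- Lowest: 0.05 × 0.30 + 0.95 × 0 = 1.5%.
- Middle: 0.20 × 0.30 + 0.80 × 0.01 = 6.8%, of which 0.008 / 0.068 = 11.8% are related-only.
- Highest: 0.50 × 0.60 + 0.50 × 0.03 = 31.5%.
- Largest related-only share: 0.95 × 0.03 / (0.015 + 0.0285) = 65.5%.

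The percentage among children under full follow-up is *p*, 30% to 60% by assumption. Over these ranges the planned table would show 1.5% to 31.5%. The figures show how the table behaves and are not estimates for this trial.

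**Step 6: ambiguities to settle.** Protocol 9.12 defines the end of the study as the last visit of the last subject, while SAP 5.2.6.1 uses a date for each child. Under either reading, routine recording stops at the child's own last visit, so the denominator problem remains. Separately, Protocol 6.2.1.4 gives the follow-up to Visit 12 as 2 weeks, against 4 weeks in Protocol 7.2.11 and in the 407-day sum. These passages must be reconciled.

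**The case against.** The strongest reply is that the SAP does what the protocol says. The open-ended TEAE definition and the related-only rule both come from the protocol and apply equally to both arms, and no adverse-event test depends on this table. The by-subject listing in SAP 5.5.1.3 shows onset day, relationship and treatment group, and SAP 5.3.1 lists each child's termination details, so a reader can separate the events. Counting late related events also fits the SAP's conservative handling elsewhere, where missing causality is treated as drug-related and missing severity as severe (SAP 5.5.1.2). All of this stands. It makes the point minor, and it argues against removing post-study related events from TEAE counts altogether. It does not repair the denominator of the late table.

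Two stronger readings are tempting, and the documents support neither.

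- A reader might infer that the related share of TEAEs after Day 407 is inflated. The SAP specifies no such share: the late table is not split by relatedness, and the tables of drug-related TEAEs have no 407-day cut.
- A reader might infer that events on active patches in the extension will be counted under placebo here and dilute the contrast between arms. Children randomised to placebo are offered DBV712 in the extension (Protocol 3.1), and nothing closes the TEAE window at the first extension dose. But the extension is a separate study, and neither document says that its events enter this database. This is a possibility to close off in wording, not a finding.

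**Conclusion.** The point holds for one table. The percentage of subjects with TEAEs after Day 407 combines full recording in delayed children with related-only recording in all others, over a denominator that includes both. It is not a late-treatment risk. The conclusion rests on the SAP 5.1 denominator convention applying, since no other is stated, and on at least some children remaining in the study past Day 407, which the SAP expects. The size of the distortion cannot be derived from the documents. The table is descriptive, efficacy is untouched, and SAP and protocol agree on the recording rule. This is a minor improvement that costs little.

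**What to change.** In SAP 5.5.1.3, restrict the table to children whose study end date (SAP 5.2.6.1) is after Day 407, and to events with onset after Day 407 and on or before that date. Use those children as the denominator, and show their number and patient time after Day 407 by arm.

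Keep related events with onset after a child's study end in the overall TEAE tables, as the protocol's definition allows, but flag them and show them on a separate line or in a separate listing. Add one sentence stating that events with onset on or after the first extension dose are not attributed to the arm randomised here. State whether the end of the study in SAP 5.5.1.1 means the child's or the trial's, and reconcile the follow-up length in Protocol 6.2.1.4.

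The cost is SAP wording, a date filter on a variable already derived, and one extra line or listing. No new data are needed. The late table will have a smaller denominator, so its percentages will be less precise.
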